### 9.2 Secondary Outcome

(1) Overall detection (yes/no): For each subject, an assessment will be made of whether there was overall sentinel node detection. A sentinel lymph node will be defined as being detected if it is detected on the pre-operative SPECT/CT imaging scan or intraoperatively using near-infrared imaging or the handheld gamma detection device. If at least one SLN is detected (on any side), then this outcome will be considered a ‘Yes’.

(2) Location and number of SLNs detected by Lymphoseek: The location and number of sentinel lymph nodes detected by Lymphoseek will be assessed. A sentinel lymph node will be defined as being detected by Lymphoseek if it is detected using the pre-operative SPECT/CT imaging scan and/or intraoperatively using the gamma detection device.

(3) Location and number of SLNs detected by Indocyanine Green: The location and number of sentinel lymph nodes detected by Indocyanine Green will be assessed. A sentinel lymph node will be defined as being detected by Indocyanine Green if it is detected intraoperatively using near-infrared imaging only and not by the gamma detection device.

(4) Adverse events and severe adverse events will be monitored and reported.

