## PROTOCOL SYNOPSIS

TITLE	Concurrent use of Lymphoseek and Indocyanine Green for sentinel lymph node detection in endometrial cancer – a prospective study
STUDY PHASE	Feasibility
INDICATION	Sentinel lymph node sampling in clinically uterine confined early-stage endometrial cancer
INVESTIGATIONAL PRODUCT OR PROCEDURE	Concurrent use of Lymphoseek and Indocyanine Green in minimally invasive surgery
PRIMARY OBJECTIVE(S)	To determine the detection rate of bilateral sentinel lymph nodes with the concurrent use of Lymphoseek and Indocyanine Green as compared to each agent alone.
SECONDARY OBJECTIVE(S)	
(1) To determine the overall detection rate of sentinel lymph nodes with concurrent use of Lymphoseek and Indocyanine Green
 
(2) To determine location and number of Lymphoseek-positive sentinel lymph nodes preoperatively by single-photon emission computed tomography (SPECT/CT imaging) and intraoperatively by a laparoscopic handheld gamma detection
 
(3) To determine the location and number of Indocyanine Green-positive sentinel lymph nodes by intraoperative infrared fluorescent imaging
 
(4) To determine the concordance of Lymphoseek-positive sentinel lymph nodes with intraoperatively detected Indocyanine Green-positive sentinel lymph nodes, and vice versa, the concordance of Indocyanine Green-positive sentinel lymph nodes with Lymphoseek-positive sentinel lymph nodes.
 
(5) To assess the safety of the concurrent use of Lymphoseek and Indocyanine Green

TREATMENT SUMMARY	
Sentinel lymph node assessment
 
 
- Preoperatively, within 24 hours prior to surgery, the subject will receive in the nuclear medicine suite of Stanford Hospital injections of 0.125 mCi or 0.5 mCi each Lymphoseek into the uterine cervix at 3, 6, 9, and 12 o'clock. Immediate and delayed static planar images will be obtained with and without a transmission source. SPECT-CT of the abdomen and pelvis will be obtained for further characterization.
 
- Subjects will then undergo minimally invasive endometrial cancer surgery. The SPECT/ CT images will be available for review to the surgeon prior to the start of the surgery.
 
- In the operating room, following anesthesia induction, the uterine cervix will be injected with 0.5 mL each of Indocyanine Green at positions of 3, 6, 9, and 12 o'clock.
 
- The surgery will start with the identification and dissection of
 

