### 1.2 Secondary Objectives

- (1) To determine the overall detection rate of sentinel lymph nodes with concurrent use of Lymphoseek and Indocyanine Green;
- (2) To determine the location and number of Lymphoseek-positive sentinel lymph nodes preoperatively by single-photon emission computed tomography (SPECT/CT imaging) and intraoperatively by a laparoscopic handheld gamma detection device and near-infra-red fluorescent imaging;
- (3) To determine the concordance of Lymphoseek-positive sentinel lymph nodes detected by SPECT/CT and/or gamma probe with intraoperatively detected Indocyanine Green-positive sentinel lymph nodes, as well as reverse concordance.
- (4) To assess the safety of the concurrent use of Lymphoseek and Indocyanine Green.

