## **4. TREATMENT PLAN**

In this study, the patient will receive cervical injections of Lymphoseek 1 – 24 hours prior to surgery and subsequent SPECT/CT imaging preoperatively. Intraoperatively, following anesthesia induction, Indocyanine Green will be injected into the uterine cervix. Using near-infrared imaging, efferent lymphatic vessels and lymph nodes will be visualized and confirmed by detected radioactivity using a laparoscopic gamma counter. The preoperatively obtained SPECT/CT images will help guide the surgery. The laparoscopic gamma counter will confirm that sentinel lymph node tissue was removed by recording gamma counts before and after lymph node removal.

Subject participation in this study comprises the following:

- Screening**

- Screening begins after informed consent is obtained.
- The screening window is Day 1 to Day 42 after signing of informed consent.
- Screening assesses the subject's eligibility to participate as determined by inclusion/ exclusion criteria.

- Sentinel lymph node assessment**

- Preoperatively, 1 - 24 hrs prior to surgery, the patient will receive in the nuclear medicine suite of Stanford Hospital injections of 0.125 mCi or 0.5 mCi mL each Lymphoseek into the uterine cervix at 3, 6, 9, and 12 o'clock. Then, the patient will undergo SPECT/ CT imaging. Immediate and delayed static planar images will be obtained with and without a transmission source. SPECT-CT of the abdomen and pelvis will be obtained for further characterization. The imaging process will take approximately 1 hour.

- The patient will undergo minimally invasive endometrial cancer surgery. The SPECT/ CT images will be available for review to the surgeon prior to the start of the surgery.
- In the operating room, following anesthesia induction, the uterine cervix of the patient will be injected with about 2.0 mL total of Indocyanine Green. The surgery will start with the identification and dissection of sentinel lymph nodes.
- **Follow up (duration of the study)**
  - The patient will be observed preoperatively after Lymphoseek injection in the nuclear medicine suite and postoperatively in the recovery room for possible allergic reactions or any other adverse events.

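### Section 9.2(3) drops every gamma-positive node from the Indocyanine Green count, so nodes that took up both tracers are scored as Indocyanine Green failures

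*Combined protocol and SAP*

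**What the plan says.** Section 9.2 defines tracer positivity node by node, and the two definitions are not symmetric.

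- Item (2), Lymphoseek: a node counts "if it is detected using the pre-operative SPECT/CT imaging scan and/or intraoperatively using the gamma detection device". The near-infrared result plays no part.
- Item (3), Indocyanine Green (ICG): a node counts "if it is detected intraoperatively using near-infrared imaging only and not by the gamma detection device".

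Other parts of the protocol bear on this:

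- Synopsis, secondary objective (3), refers to "Indocyanine Green-positive sentinel lymph nodes by intraoperative infrared fluorescent imaging", with no gamma exclusion.
- Section 1.2, objective (3), compares Lymphoseek-positive nodes "with intraoperatively detected Indocyanine Green-positive sentinel lymph nodes, as well as reverse concordance". Synopsis objective (4) likewise asks for concordance in both directions.
- Section 4 describes the operation: under near-infrared imaging, "efferent lymphatic vessels and lymph nodes will be visualized and confirmed by detected radioactivity using a laparoscopic gamma counter". Section 2.3 gives the gamma counter the same confirming role.
- Section 11.5.2 counts patients with nodes found by each tracer and applies a McNemar or mid-p McNemar test.
- The synopsis, but not Section 1.1, words the primary objective as bilateral detection "with the concurrent use of Lymphoseek and Indocyanine Green as compared to each agent alone".

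**The concern.** Taken literally, item (3) counts nodes that near-infrared found and the gamma probe did not. That is a different quantity from nodes detected by ICG. A node positive on both devices is the intended result of the procedure, yet the rule scores it as a Lymphoseek success and an ICG failure.

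Concordance needs nodes that can be positive for both tracers, and the rule bars every gamma-positive node from being one. The results at stake are the number and location of ICG nodes, the concordance objective and the McNemar comparison. An ICG-alone rate for the synopsis version of the primary objective would also be affected if it used this definition, which is the only definition of ICG detection in Section 9.

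**Working it through.** **The plan's own figures.** For n = 30 with at least 24 successes, the exact binomial tail is 0.607 at a true rate of 80% and 0.133 at 69%. The exact 95% interval for 24/30 is 61.4% to 92.3%. These match the 61%, 13% and 61% to 92% in Section 11.6.2 and do not use the ICG definition. The documents give no expected figure for ICG counts or concordance.

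**Logic of the definitions.** Let N, G and S mean positive on near-infrared, gamma probe and SPECT/CT.

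- Lymphoseek-positive = S or G.
- ICG-positive as written = N and not G.
- Positive for both as written = (N and not G) and (S or G) = N and S and not G.
- Positive for both if ICG-positive simply means N = N and (S or G).

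The difference is every node with N and G. Each one moves from both tracers to Lymphoseek only. The only double-positive node that survives is positive on near-infrared and SPECT/CT but negative on the gamma probe.

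**Node-level example (invented counts).** Take 20 nodes positive on near-infrared and gamma, 5 on near-infrared only and 5 on gamma only, with SPECT/CT adding nothing.

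- All fluorescent nodes counted: ICG = 20 + 5 = 25, of which 20/25 (80%) are concordant.
- As written: ICG = 5, of which 0/5 are concordant.

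**Patient-level example (extreme case).** In 20 women whose nodes are all near-infrared- and gamma-positive, the tracers agree perfectly. As written they give 20 versus 0 discordant pairs, with exact McNemar p = 2 × 0.5^20 = 1.9 × 10^-6.

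**Illustration anchored on the protocol's rates.** Assumptions:

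- 30 women with one node each, so that node and patient level coincide.
- ICG 88%, the institutional overall rate in Section 2.1.
- Lymphoseek 92%, the lower end of the 92–96% in Section 2.1.1. Those are technetium colloids, used here as a proxy.
- The two tracers are independent.

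Rounded counts: ICG 0.88 × 30 = 26; Lymphoseek 0.92 × 30 = 28; both 0.88 × 0.92 × 30 = 24. That leaves Lymphoseek only 28 − 24 = 4, ICG only 26 − 24 = 2, neither 0. The rule as written then moves the gamma-positive share of the 24 into Lymphoseek only.

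| ICG rule | Double-positives that are gamma-positive | Both | Lymphoseek only | ICG only | ICG rate | Agreement | Exact McNemar p |
|---|---|---|---|---|---|---|---|
| Near-infrared, regardless of gamma | any | 24 | 4 | 2 | 26/30 (87%) | 24/30 (80%) | 0.69 |
| As written | 100% | 0 | 28 | 2 | 2/30 (7%) | 0/30 (0%) | 8.7 × 10^-7 |
| As written | 80% | 5 | 23 | 2 | 7/30 (23%) | 5/30 (17%) | 1.9 × 10^-5 |
| As written | 50% | 12 | 16 | 2 | 14/30 (47%) | 12/30 (40%) | 0.0013 |

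**Range.** Lymphoseek was varied from 80% to 96% and overlap from independence to its maximum. Counting all fluorescent nodes gives ICG 87% and agreement 73–100%. The rule as written, with all double-positives gamma-positive, gives ICG 0–17% and agreement 0–13%.

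**The case against.** The strongest defence is that items (2) and (3) merely list which device counts for which tracer: SPECT/CT and gamma for Lymphoseek, near-infrared alone for ICG. The synopsis objective and the two-way concordance objective fit that reading, since both presuppose overlap. It may be what was meant. But the clause excluding the gamma device reads more naturally as a condition on the node, and nothing elsewhere in the protocol overrides it. Two analysts could obtain 87% and 7% from the same data, so the sentence has to change under either reading.

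Several limits stand:

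- Node-level concordance is biased downwards but is not necessarily zero, because nodes positive on near-infrared and SPECT/CT but gamma-negative still count for both.
- The McNemar test works on patients. A woman with one gamma-positive node and a different near-infrared-only node is positive for both tracers, so that cell need not be empty. The 20-versus-0 table is the extreme.
- The size depends heavily on an overlap that the documents do not state.
- No section ties an ICG-alone rate to item (3), so the effect on the synopsis comparison is conditional.
- The primary outcome (Section 9.1) and overall detection (Section 9.2 item (1)) accept any of the three modalities and are untouched, as are the 80% decision rule and safety.

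**Conclusion.** The concern holds. Applied as written, Section 9.2(3) gives wrong ICG counts and locations, understated concordance in both directions and a McNemar table tilted against ICG. It also conflicts with synopsis objective (3) and with the concordance objectives.

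The direction of the bias follows from the definitions alone. Its size does not: in the 88%/92% illustration the reported ICG rate falls from 87% to between 7% and 47%, and agreement from 80% to between 0% and 40%, as the gamma-positive share of double-positive nodes goes from all to half. Those figures rest on one node per woman, independence and a colloid proxy for Lymphoseek. The damage is confined to secondary outcomes, plus the synopsis comparison with each agent if it uses this definition. It should be corrected before analysis because a stated objective cannot be validly answered under the present wording.

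**What to change.** Reword Section 9.2(3) so that a node is detected by ICG if it is seen intraoperatively on near-infrared imaging, regardless of its SPECT/CT or gamma result. Report three separate classes: both tracers, ICG only and Lymphoseek only. Behind them, give the full cross-table of near-infrared against SPECT/CT and gamma, with the proportion of Lymphoseek-positive nodes that are ICG-positive and the reverse. Those proportions answer the concordance objective directly; McNemar's test compares the two marginal detection rates and does not measure concordance.

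The cost is one sentence in the protocol and no added procedure, since the Section 8 calendar already schedules both intraoperative modalities and Section 4 records gamma counts before and after node removal. One check is needed: the documents do not show that the case report form holds a near-infrared result for each node. If it captures only the item (3) classification, a field for each modality per node must be added.

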## 10. REGULATORY CONSIDERATIONS

### 10.1 Institutional Review of Protocol

The protocol, the proposed informed consent and all forms of participant information related to the study (e.g. advertisements used to recruit participants) will be reviewed and approved by the Stanford IRB and Stanford Cancer Institute Scientific Review Committee (SRC). Any changes made to the protocol will be submitted as a modification and will be approved by the IRB prior to implementation. The Protocol Director will disseminate the protocol amendment information to all participating investigators.

### 10.2 Data and Safety Monitoring Plan

The investigators will review AEs and SAEs in real time and report these events according to the Stanford Cancer Center Cancer Clinical Trials Office Standard Operating procedures.

The Stanford Cancer Institute Data and Safety Monitoring Committee (DSMC) will be the

monitoring entity for this study. The DSMC will audit study-related activities to determine whether the study has been conducted in accordance with the protocol, local standard operating procedures, FDA regulations, and Good Clinical Practice (GCP). This may include review of the following types of documents participating in the study: regulatory binders, case report forms, eligibility checklists, and source documents. In addition, the DSMC will regularly review serious adverse events and protocol deviations associated with the research to ensure the protection of human subjects. Results of the DSMC audit will be communicated to the IRB and the appropriate regulatory authorities at the time of continuing review, or in an expedited fashion, as needed.

### **10.3 Data Management Plan**

The Protocol Director, or his/her designee, will prepare and maintain adequate and accurate participant case histories with observations and data pertinent to the study. Study specific Case Report Forms (CRFs) will document outcomes for data analysis. Case report forms will be developed and maintained both on paper and electronically using the REDCap database system by the clinical research team. CRFs will be kept in a locked office, only accessible to the research team.

## **11. STATISTICAL CONSIDERATIONS**

### **11.1 Statistical Design**

This is an open-label, single cohort, feasibility study to assess the detection rate of bilateral sentinel lymph nodes with concordant use of Lymphoseek and Indocyanine Green in patients with endometrial cancer.

### **11.2 Interim analyses**

No interim analysis will be conducted.

### **11.3 Descriptive Statistics and Exploratory Data Analysis**

We will provide descriptive statistics for the study population. The primary and secondary outcomes will be summarized using frequencies and percentages.

### **11.4 Primary Analysis**

#### **11.4.1. Analysis Population**

The analysis population will include all patients who complete the study procedures specified above. We do not expect missing data or loss-to-follow up since the outcome is ascertained at the time of surgery. Patients who do not adhere to the study treatment plan of both injections, SPECT/CT and surgery will not be included in the analysis.

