### 2.1.1 Tracers for sentinel lymph node detection

Historically, sentinel lymph node sampling was first described in the late 70's for penile cancer using the injection of radiocolloids [8]. Subsequently, sentinel lymph node sampling has become standard of care in cutaneous melanoma and breast cancer [9, 10]. Vulva cancer was the first gynecologic malignancy where sentinel lymph node sampling was tested [11, 12]. The role of sentinel lymph node mapping in endometrial carcinoma is under evaluation [13].

In endometrial cancer, as in all other cancer entities, radioactive tracers, or dyes, either non-fluorescent or fluorescent, or combinations of radioactive tracers and dyes have been employed. The radioactive tracers used are filtered or non-filtered sulfur colloids, most commonly radiolabeled with technetium-99m (Tc 99m). The major advantage of radioactive tracers is deep tissue penetration and the ability to detect sentinel lymph node locations preoperatively. Reported overall detection rates are 92-96% with a bilateral detection rate of 73-80% [14, 15]. Concerns regarding the use of radioactive colloids are (i) the unspecific and passive distribution of the tracer colloids throughout the lymphatic system by lymph flow and/or diffusion which diminishes the retention of the tracer in the first draining lymph node and results in the leakage of radiotracers to subsequent lymph nodes and thereby the detection of the second or third lymph node stations instead of the actual sentinel lymph node; (ii) the need for preoperative injection and imaging; and (iii) the handling of radioactivity.

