## 9. MEASUREMENTS

### 9.1 Primary Outcome

Bilateral SLN Detection (yes/no): For each subject, an assessment will be made of whether there was bilateral sentinel lymph node detection. A sentinel lymph node will be defined as being detected if it is detected on the pre-operative SPECT/CT imaging scan or intraoperatively using near-infrared imaging or the handheld gamma detection device. If at least one SLN is detected on each side, then this outcome will be considered a ‘Yes’.

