### **11.4.2. Analysis Plan**

The analysis for this study is primarily descriptive as the primary objective is to determine the detection rate of bilateral SLNs. The bilateral SLN detection rate will be calculated as the number of patients with bilateral SLN detection divided by the total number of patients. If the bilateral detection rate is at least 80%, we will deem this approach promising in detecting bilateral SLNs.

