## **11.5. Secondary Analysis**

### **11.5.1 Analysis Population**

The population for secondary analysis will include all patients in the safety population, i.e. the analysis population plus those women who underwent lymphoseek injection but were removed from the study for any reason.

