### **11.5.2 Analysis Plan**

Descriptive statistics will be used to analyze the secondary outcomes. The overall detection rate of sentinel lymph nodes will be calculated as the number of patients with overall SLN detection divided by the total number of patients. To assess the safety of the concurrent use Lymphoseek and Indocyanine Green, we will calculate the number and rate of adverse events. We will describe the location and number of Lymphoseek-positive SLNs by method of detection (pre-operative or intraoperative). We will calculate the number of patients with SLNs found by Lymphoseek and by Indocyanine Green and conduct a McNemar's test (or mid- $p$  McNemar's test) to determine the concordance of Lymphoseek-positive and Indocyanine Green-positive sentinel lymph nodes.

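### Bilateral detection is analysed in completers and overall detection in the wider safety population, so two nested rates can have different denominators, and no analysis tests the 80% call against the excluded women

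*Combined protocol and SAP*

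**What the plan says.** **Primary population (11.4.1).** "Patients who do not adhere to the study treatment plan of both injections, SPECT/CT and surgery will not be included in the analysis". The section adds that no missing data are expected, because the outcome is established at surgery.

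**Primary rate (11.4.2).** The rate is the "number of patients with bilateral SLN detection divided by the total number of patients". An observed rate of at least 80% is called promising.

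**Secondary population (11.5.1).** "The population for secondary analysis will include all patients in the safety population", which is defined as "the analysis population plus those women who underwent lymphoseek injection but were removed from the study for any reason". This is not limited to adverse events.

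**Overall rate (11.5.2).** The rate is the "number of patients with overall SLN detection divided by the total number of patients". Neither rate restates which patients make up its total.

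**Outcome definitions (9.1, 9.2).** A node counts as "detected if it is detected on the pre-operative SPECT/CT imaging scan or intraoperatively", by near-infrared imaging or the gamma probe. Bilateral detection needs a node on each side; overall detection needs a node on either side.

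**Sample size (11.6.2).** With 30 participants and a cut-off of 24, the stated probability of a promising call is 61% at a true 80% and 13% at a true 69%. No replacement rule is given.

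**Removal (4.1).** Removal is described as cancelling the tilmanocept injection and the scan. One listed reason is metastatic disease found in the operating room. Sections 4 and 8 place the injection and scan before surgery.

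**The concern.** Every woman with bilateral detection also has overall detection, so readers will set the two rates side by side. Read by section heading, the plan divides the first by completers and the second by completers plus women removed after injection. One removal is enough to make the totals differ, and the gap between the rates then mixes mapping performance with a change of denominator.

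The trial has one decision rule, applied to about 30 patients, and each patient is worth about three percentage points. The call can therefore turn on a few excluded women. Some of them may already have an observed primary outcome, because detection on the preoperative scan alone counts under 9.1. The plan discards that outcome from the bilateral rate, and no analysis shows whether this matters.

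**Working it through.** **Inputs.** N = 30, cut-off 24, rates 80% and 69% (11.6.2); the 80% rule (11.4.2); populations (11.4.1, 11.5.1). The number excluded, m, is not given; m = 1 to 3 is an assumption.

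**Step 1: the plan's own figures.** Exact binomial P(X ≥ 24), n = 30: 0.607 at p = 0.80 and 0.133 at p = 0.69. These match the stated 61% and 13%.

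**Step 2: 30 injected, m excluded, none replaced.** If x of the 30 − m completers are bilateral and j of the m excluded women are bilateral (j = 0 to m), the rates are x/(30 − m) in completers and (x + j)/30 in all injected women.

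| m | Completer rate | Call | Rate over 30, j = 0 to m |
|---|---|---|---|
| 1 | 24/29 = 82.8% | promising | 80.0%, 83.3% |
| 1 | 23/29 = 79.3% | not | 76.7%, 80.0% |
| 2 | 23/28 = 82.1% | promising | 76.7%, 80.0%, 83.3% |
| 2 | 22/28 = 78.6% | not | 73.3%, 76.7%, 80.0% |
| 3 | 22/27 = 81.5% | promising | 73.3%, 76.7%, 80.0%, 83.3% |
| 3 | 21/27 = 77.8% | not | 70.0%, 73.3%, 76.7%, 80.0% |

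With one exclusion the completer rule can only hide a promising call. With two or three, the two analyses can disagree in either direction.

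**Step 3: 30 completers plus one further injected woman who is removed.** 24/30 = 80.0% is promising; over 31 it is 24/31 = 77.4% if she is not bilateral. In the other direction, 23/30 = 76.7% can reach at most 24/31 = 77.4%. On this reading a call can only be lost.

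**Step 4: fewer than 30 analysed, no replacement, loss unrelated to mapping.** The cut-off is the smallest whole number at or above 0.8n.

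| n | Cut-off | P(promising) at 80% | P(promising) at 69% |
|---|---|---|---|
| 30 | 24 | 60.7% | 13.3% |
| 29 | 24 | 46.3% | 7.6% |
| 28 | 23 | 50.1% | 9.3% |
| 27 | 22 | 53.9% | 11.3% |

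The loss is mainly in the chance of success at a true 80%; the error at 69% falls.

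**Step 5: loss related to mapping.** Let q be the detection probability in the excluded women. With m = 3 of 30 and a 69% average over all 30, the completer rate is (30 × 0.69 − 3q)/27. At q = 0 this is 0.767, and P(X ≥ 22 of 27) = 37%. At q = 0.69 the probability is 11%. At q = 1 it is 5.7%. The documents do not say which value of q applies.

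**The case against.** **The primary population fits the question.** The objective concerns concurrent use of both agents in a descriptive feasibility study. A woman who never reaches surgery or receives Indocyanine Green is arguably outside it. This stands, and it is why the completer analysis should remain primary and the all-injected analysis be a sensitivity analysis only.

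**Losses after injection are probably few.** Injection is 1 to 24 hours before surgery and the plan expects no missing data. A woman found to have metastatic disease in the operating room may have had both injections, the scan and surgery, and so still qualify under 11.4.1. This also stands: three exclusions is an assumption. But 11.5.1 itself provides for women removed after injection, so the plan does foresee them.

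**The split may be unintended.** The synopsis names only one analysis population, so a shared denominator may have been meant. If so, 11.5.1 needs correcting.

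**Stronger readings that the documents do not support.** A reader might infer that the completer rule flatters the result. Exclusion is for non-completion, not failed mapping, and step 5 shows that the effect can go either way. A reader might also expect the bilateral rate to exceed the overall rate. That is arithmetically possible: with 24/27 = 88.9% bilateral and 25 of the 27 having any node, overall over 30 is 83.3% or 86.7% if none or one of three removed women has a node. But this split is favourable to reversal. Even then, if removed women are detected at the institution's 88% overall rate (2.1), none or one of three has probability 0.12³ + 3 × 0.88 × 0.12² = 4.0%. Reversal mainly needs removal before imaging and should not carry the argument.

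**Conclusion.** The point holds in a limited form and should be corrected before results are known. As written, bilateral and overall detection have different denominators once one injected woman is removed, and nothing planned shows whether the 80% call depends on the excluded women.

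The size depends on two things the documents do not give: how many are excluded, and whether 30 means injected or completed. With 30 injected and no replacement, one exclusion can only hide a promising call; two or three can change it either way. With 30 completers and one further woman removed, a call can only be lost. If nobody is excluded there is no effect.

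A reader might infer that the 61% and 13% are wrong, or that one exclusion can move the call in both directions. Neither follows: the figures are exact for 30 analysed patients, and one exclusion acts in a single direction on either reading of N. The populations are read from the section headings, since the total in each rate is undefined.

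**What to change.** 1. In 11.4 and 11.5, report bilateral and overall detection in the 11.4.1 population, and keep the 11.5.1 safety population for adverse events.
2. Add one sensitivity analysis of both rates in all Lymphoseek-injected women, classified by 9.1 and 9.2: not detected unless the scan or surgery meets the definition. Report how many had neither scan nor surgery, because counting them as not detected makes the rate a lower bound. State whether the 80% call changes.
3. In 11.6.2, say that 61% and 13% apply to 30 analysed patients and whether non-completers are replaced. If fewer are analysed without replacement, restate the cut-off and probabilities: 46%/7.6% at 29, 50%/9.3% at 28, 54%/11.3% at 27.
4. Reconcile 4.1 with sections 4 and 8. Cancelling the injection and scan cannot follow an operating-room finding, and the conflict affects who is counted.

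The cost is revised wording and one analysis of data already collected. The sensitivity rate, or a restated 61%, may look less favourable.
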